6.3. End of Treatment Visit

When the subject meets any one of the reasons for end of study treatment, relevant study procedures for end-of-treatment visit need to be performed. At the end of treatment (premanent discontinuation of both of the drugs (SHR-1210 and apatinib) is required in experimental arm), the end-of-treatment visit will start and the following examinations/procedures need to be performed

- Subject's self-evaluation results: all the subjects will complete EORTC QLQ-C30 questionnaires prior to any other study evaluation at clinical centers;
- Hematology: including complete blood count and category (white blood cell, red blood cell, lymphocyte, monocyte, neutrophil, basophil, eosinophil), hemoglobin, platelet count;
- Urinalysis: including white blood cell, red blood cell, urine protein. In case urine protein is $\geq 2+$, 24h urine protein quantification must be added;

- Blood biochemistry: including ALT, AST, total bilirubin, γ -glutamyl transferase (GGT), direct bilirubin, indirect bilirubin, ALP, LDH, albumin, blood urea nitrogen or serum urea, creatinine, blood glucose, amylase (lipase test needs to be added if amylase level is abnormal and clinically significant);
- Blood electrolytes: including potassium, sodium, chlorine, calcium, magnesium, phosphorus;
- 12-lead ECG (measured after sitting still for at least 5 minutes): heart rate and QTc interval (calculated using Fridericia's formula);
- ECOG-PS score (see APPENDIX 2 for details);
- Perform a careful, comprehensive physical examination: weight, head and face, skin, lymph nodes, eye, ear, nose, throat, mouth, respiratory system, cardiovascular system, abdomen, genitourinary system, musculoskeletal, neurological and mental status. In addition, physical examination of reactive capillary endothelial proliferation needs to be performed on the experimental arm;
- Vital signs (performed after sitting still for 5 minutes): including temperature, blood pressure, pulse rate and respiratory frequency;
- Fecal occult blood test;
- Thyroid function (FT3, FT4, TSH);
- Coagulation parameters: including INR and/or PT (if INR can not be collected, PT will be used as the basis for judgment);
- Serum human chorionic gonadotropin (HCG) test for female subjects of childbearing potential;
- Collect concomitant medications/therapies;
- Collect adverse events;
- Tumor imaging evaluation;
- Verification and recovery of subject diary.

If 12-lead ECG, routine laboratory tests (including hematology, urinalysis, serum biochemistry, serum electrolyte, coagulation parameters, thyroid function, fecal occult blood and virology tests, AFP) are completed within 7 days before withdrawal, these tests would not be necessary in this visit again.

6.4. Follow-up Period

Follow up period is initiated when the end-of-treatment visit is completed. 30 days (± 7 days) after the last dose of study drug, subjects must return to the study center for safety follow-up and complete the following parameters for safety evaluation, regardless of initiation of new antitumor therapy. The telephone follow-up will be performed 60 days (± 7 days) and 90 days (± 7 days) after the last dose of study drug, only the survival status, subsequent antitumor therapy, concomitant medication/therapy and AEs/SAEs within the timeframe specified in the protocol need to be collected. If the subject could not resume study drug for AE, the latest date of

administration is used as the date of last dose. If the date has exceeded 30 days (+7 days) over the date when the subject needs to be withdrawn from the study treatment by judgment, the situation does not need to be recorded as deviation from protocol but the subject is recommended to return to the study site as soon as possible for safety visit.

- Hematology: including complete blood count and category (white blood cell, red blood cell, lymphocyte, monocyte, neutrophil, basophil, eosinophil), hemoglobin, platelet count;
- Urinalysis: including white blood cell, red blood cell, urine protein. In case urine protein is $\geq 2+$, 24h urine protein quantification must be added;
- Blood biochemistry: including ALT, AST, total bilirubin, γ -glutamyl transferase (GGT), direct bilirubin, indirect bilirubin, ALP, LDH, albumin, blood urea nitrogen [BUN] or serum urea, creatinine, blood glucose, amylase (lipase test needs to be added if amylase level is abnormal and clinically significant);
- Blood electrolytes: including potassium, sodium, chlorine, calcium, magnesium, phosphorus;
- 12-lead ECG (measured after sitting still for at least 5 minutes): heart rate and QTc interval (calculated using Fridericia's formula);
- ECOG-PS score (see APPENDIX 2 for details);
- Weight and physical examination of important sites: cutaneous system, respiratory system, cardiovascular system, abdomen and mental state. In addition, physical examination of reactive capillary endothelial proliferation needs to be performed on the experimental arm;
- Vital signs (performed after sitting still for 5 minutes): including temperature, blood pressure, pulse rate and respiratory frequency;
- Thyroid function (FT3, FT4, TSH);
- Coagulation parameters: including INR and/or PT (if INR can not be collected, PT will be used as the basis for judgment);
- Serum human chorionic gonadotropin (HCG) test for female subjects of childbearing potential;
- Collect concomitant medications/therapies;
- Collect adverse events;
- Tumor imaging evaluation (applicable for the subjects who have not achieved radiological progression at the end of study treatment);
- Collect data on survival;
- Collect subsequent antitumor therapy.

After the end of safety follow-up, the subjects will enter survival follow-up period. Investigators must follow up subject's survival every 30 days (± 7 days), until death,

loss of follow-up, termination of study by the sponsor or reaching other criteria for end of study, whichever comes first. Investigators can inquire the subject, his/her family members or local physician via phone, collect subject's survival information (death and reason of death) and data on other tumor therapies after the end of study treatment. The data on each survival follow-up needs to be recorded in detail in the original medical record.

Subjects who end study treatment for toxicity or other reasons with no radiological progression observed still need to receive radiological evaluation according to the original frequency, until progression of disease or start of other antitumor therapy, the radiological evidence on PD should be obtained from such subjects as much as possible.

All the treatment-related toxicities must be followed up until they are resolved, recovered to baseline or considered as irreversible. AE should be reported and recorded according to the requirement during safety follow-up.

6.5. Unscheduled Visits

For unscheduled visits (e.g., due to AEs) that occur or are needed before the end of study, the following items should be recorded:

- Visit date;
- Reason for visit;
- Concomitant medications/therapies (within the collocation period specified in the protocol);
- AEs (within the collocation and follow-up period specified in the protocol);
- All the relevant examinations performed (including imaging examination, if any);
- Whether the subject can continue or resume study treatment, if yes, record the dose administered.

6.6. Treatment Beyond Progression

If the subject has progression as defined in RECIST v1.1, he/she still can continue SHR-1210 alone or combined with apatinib (experimental arm) when he/she can still clinically benefit from and tolerate study treatment, as evaluated by investigators.

6.6.1. Criteria on Post-Progression Continuation of SHR-1210 Alone or Combined With Apatinib in Subjects in Experimental Arm

A part of patients receiving immunotherapy can still clinically benefit following radiological progression. Although the tumor is enlarged, obvious necrosis or degeneration can appear inside the tumor, decreased density inside the tumor foci can be shown on CT, it is generally considered that the patient may benefit under this circumstance. After progression of disease as defined by RECIST v1.1, subjects meeting all of the following criteria may continue with the study treatment. If the disease progression defined by irRECIST is confirmed in a subsequent radiological evaluation, the study treatment will be terminated, unless the investigator considers that the subject can continue to benefit clinically (which has to be further discussed

with and agreed by the sponsor); in the latter case, the subject may continue with the study treatment until the investigator determines that the subject can no more benefit clinically from the study treatment. Subjects who continue the dose following PD will receive periodic visit and efficacy evaluation according to the visit schedule specified in the trial.

- Investigators judge continuation of study treatment meets the best interest for the subject, and the subject does not need to start other antitumor therapy immediately;
- The subject can tolerate study treatment;
- Stable ECOG-PS score (≤ 1);
- No significant clinical symptom/sign of progression of disease, including change in laboratory examination parameters;
- Non-rapid progression of disease and progression not involving major organs/sites (e.g., spinal cord compression);
- The study treatment can be continued upon the review and approval by the medical monitors from the sponsor.

6.6.2. Other Precautions for Post-Progression Continuation of Treatment

The clinical benefit evaluation must take clinical exacerbation, continued benefit from the treatment into consideration. It is advisable to discuss with the sponsor about the decision on post-progression continuation of treatment, as judged by investigators.

If a decision is made that the subject needs to continue study treatment following progression, the subject should be treated, evaluated and followed up as required in the protocol.

The subjects who continue the treatment after PD must be sufficiently informed and sign the informed consent form for post-PD continuation of treatment: possible alternative therapies, potential risks with continuation of the treatment.

If the subject terminates the treatment for a global deterioration of health status and has no objective evidence on progression of disease, the progression will be reported as symptomatic deterioration. Every effort should be made to obtain the objective evidence on progression in these subjects after termination of the study treatment (e.g., radiological confirmation).

7. EVALUATION

7.1. Efficacy Evaluation

The efficacy endpoints include:

- Progression-free survival (PFS): defined as the length of time from the date of randomization to the first occurrence of progression or death, whichever comes first, evaluated by the BIRC or investigator based on RECIST v1.1 or irRECIST.
- Overall survival time (OS): defined as the length of time from randomization to death for any cause.

As well as the following efficacy endpoints evaluated by the BIRC or investigator based on Response Evaluation Criteria in Solid Tumors Version 1.1 (RECIST v1.1) and investigator based on the immune-related RECIST (irRECIST):

- Objective response rate (ORR): defined as the percentage of subjects with complete remission (CR) or partial remission (PR) evaluated by the BIRC or investigator based on RECIST v1.1, or irRECIST.
- Disease control rate (DCR): defined as the percentage of subjects with complete remission, partial remission or stable disease (SD) ≥ 8 weeks evaluated by the BIRC or investigator based on RECIST v1.1, or irRECIST.
- Duration of response (DoR): defined as the length of time from the date of first record of objective response (CR or PR) to the first occurrence of progression or death, whichever comes first, evaluated by the BIRC or investigator based on RECIST v1.1, or irRECIST.
- Best overall response (BOR): defined as the best response parameter between the date from randomization to objectively recorded progression or subsequent antitumor therapy, whichever comes first. For subjects with no progression or subsequent antitumor therapy documented, BOR will be determined based on all the response evaluation results.

7.2. Tumor Imaging Evaluation

7.2.1. Tumor Evaluation Based on RECIST v1.1, and irRECIST.

RECIST v1.1 (investigator and BIRC evaluated), irRECIST (only investigator evaluated) will be used for evaluation of tumor response in this study, see APPENDIX 1 for the evaluation criteria.

The tumor evaluation in screening period (at baseline) should include the enhanced CT scan of thorax, abdomen and pelvis. CT scan requires intravenous contrast agent and will scan the whole liver area, at least including 1) hepatic arterial phase and 2) portal venous phase. Enhanced MRI can be used in case of contraindications for CT contrast agent. The enhanced MRI of the whole liver should at least include 1) hepatic arterial phase and 2) portal venous phase. Cranial enhanced CT or enhanced MRI has to be performed at baseline as well. Systemic bone scan should be performed for subjects with known bone metastasis or suspected bone metastasis (exempted in case bone scan is performed within 42 days prior to randomization), the bone lesions need to be evaluated and followed up after treatment. If clinically indicated, tumors at other sites can be evaluated.

Provision on selection of target lesions: if there are no more than two target lesions in each organ, and the total number of lesions is not more than 5, more organs involved in tumors should be covered as far as possible. At baseline, the number and location of the target lesion, the major diameter of each target lesion (except lymph node) and the minor diameter of lymph node lesion, as well as the sum of diameters of all lesions should be recorded.

The baseline evaluation and post-treatment efficacy evaluation should be performed using the same method and by the same investigator as far as possible. Following

randomization, the tumor evaluation will be performed once every 8 weeks (56 ± 7 days) in the first 48 weeks, and once every 12 weeks (84 ± 7 days) afterwards. In the absence of a determined progression of the disease, tumor evaluation should be continued, regardless of whether the subject has terminated the study, until the subject dies, withdraws the informed consent, initiates subsequent antitumor therapy or terminated the study by sponsor, whichever comes first. Tumor evaluation during treatment includes CT scan of thorax, abdomen, pelvis and site of lesions; cranial CT/MRI and bone scan can be performed only when clinically indicated. Each tumor evaluation must cover all the target lesions, and all the non-target lesions if there are no special circumstances.

Further guidance and recommendations on image acquisition are provided in the Image Acquisition Guidelines.

When clinically indicated, investigators can perform unscheduled tumor evaluation. Throughout the study, each subject must use the same procedure of radiological examination. Investigators must review the results prior to the next cycle of therapy. The subjects who have achieved remission (complete remission or partial remission) for the first time need to be confirmed through the next scheduled evaluation or repeated evaluation ≥ 4 weeks after the first evaluation. The progression of disease that is suspected as pseudoprogression must be confirmed in subsequent radiological examinations, the time of the radiological examination for confirmation is at least 4 weeks after disease progression is detected or at the next scheduled time point (not exceeding 12 weeks), and prior to the termination of study treatment. Patients who meet RECIST v1.1 criteria for progression will continue to receive tumor evaluation, until progression of disease (in accordance with the irRECIST definition) or end of study treatment, whichever comes later.

Once progressive disease occurs, a physical examination of the subject and imaging confirmation is required at all times, rather than waiting for the next planned imaging examination. If the unplanned imaging findings do not meet the RECIST V 1.1 criteria of progressive disease, follow-up examinations should still be performed on the original date for the next imaging examination, unless the next planned examination is less than 14 days of this one.

If there has not been any disease progression confirmed by a radiological examination when the subject is about to withdraw from the study, it is recommended that a radiological examination be performed in time before the withdrawal (if the time from the last radiological examination to the withdrawal is ≤ 4 weeks, additional radiological examination will not be required at the time of withdrawal).

7.3. Safety Evaluation

7.3.1. Pregnancy Testing

Serum pregnancy test will be performed within 7 days prior to the start of administration for female subjects of childbearing potential. After obtaining the negative result of pregnancy test in screening period, appropriate contraceptive measures should be taken. The subject will be withdrawn from the trial if HCG test is positive.

7.3.2. Adverse Events

The evaluation of AE includes type, incidence, severity (in accordance with NCI-CTCAE v4.03), start and end time, correlation with SAE and prognosis.

7.3.3. Laboratory Safety Evaluation

Blood and urine samples will be collected in accordance with the study flow chart, analyzed and detected in local laboratory. The items of laboratory tests are shown in Table 8.

Table 8. Items of Laboratory Tests

| Item | Contents |
|-------------------------------------|---|
| Hematology | Complete blood cell count and category (white blood cell, red blood cell, lymphocyte, monocyte, neutrophil, basophil, eosinophil), hemoglobin, platelet count. |
| Blood Biochemistry/ Electrolytes | Including hepatic function (ALT, AST, TBIL, ALP, GGT, direct bilirubin and indirect bilirubin), renal function (BUN or serum urea, creatinine), albumin, amylase (lipase test must be added if amylase level is abnormal and clinically significant), blood glucose, LDH; potassium, sodium, calcium, phosphorus, magnesium, chlorine. |
| Coagulation Parameters | INR and/or PT (if INR can not be collected, PT will be used as the basis for judgment) |
| Urinalysis | Including white blood cell, red blood cell, urine protein. It will be detected within 72h prior to administration at each visit. If urine protein is $\geq 2+$, 24h urine protein quantification must be added. |
| Thyroid Function | TSH, FT3, FT4 |
| Virology | HIV-Ab, HBV and HCV infection test. Requirement for HBV test: HBV five serological markers (HBsAg, HBsAb, HBcAb, HBeAg, HBeAb) will be detected, if HBsAg or HBcAb is positive, HBV-DNA will be quantified. Requirement for HCV test: HCV-Ab will be detected as to determine the presence of HCV infection, if HCV-Ab is positive, HCV-RNA will be quantified. |

7.3.4. Physical Examination and Vital Signs

Physical examination includes height (first collection only), weight, head and face, skin system, lymph nodes, eye, otolaryngology, mouth, respiratory system, cardiovascular system, abdomen, genitourinary system, musculoskeletal, neurological and mental status. The items of physical examination at different time points are provided in Section 6 in detail.

Vital signs include temperature, blood pressure (which needs to be measured and recorded at least twice to get the mean value as the blood pressure value), pulse rate and respiratory frequency (performed after sitting still for 5 minutes).

In addition, physical examination of reactive capillary endothelial proliferation needs to be performed on the experimental arm.

7.3.5. 12-lead ECG

Heart rate and QTc interval (calculated using Fridericia formula: $QTcF = QT/$

($RR^{0.33}$), RR is the normalized heart rate and is calculated as 60 divided by heart rate).

7.3.6. Echocardiography

Including LVEF evaluation.

7.3.7. ECOG-PS scores

Criteria for ECOG-PS score can be found in APPENDIX 2.

7.4. Patient Reported Outcomes (PRO)

All the subjects will complete EORTC QLQ-C30 questionnaires prior to the administration of study drug and conduction of any other study evaluation at the clinical center from Day 1 of Cycle 1, then repeat the above procedure on Day 1 of every two cycles in the first 12 cycles, and Day 1 of every three cycles afterwards, until end-of-treatment visit (inclusive). Questionnaires for PRO evaluation should be validated and in subjects' local language. The questionnaires will be paper-based in this study.

Questionnaires should be completed prior to initiation of any pertinent study visit which involves other study activities (including the study treatment) and contact with the investigator, to ensure that the results are not influenced by the interaction between the subject and the investigator. Provide subjects with a quiet place and advise them to complete within 30 minutes. The study site should make every effort to ensure that a complete questionnaire is obtained from each subject at each scheduled time point, so as to avoid any delay in clinical evaluations.

If there are privacy requirements for filling out questionnaires in local regulations (e.g., if the questionnaire is not supposed to be seen by the clinical staff), the study site should make appropriate arrangements to ensure that the requirements are met as far as possible.

7.4.1. EORTC QLQ-C30

EORTC QLQ-C30 is a core scale in the quality of life measurement questionnaire system for all cancer patients that is systematically developed by European Organization for Research and Treatment of Cancer, and used for measurement of quality of life in all the cancer patients (for the common part). The questionnaire is comprised of 5 functional scales (somatic, role, cognitive, emotional, social), 4 symptom scales (fatigue, pain, nausea, vomiting), one global health status scale and several separate items (including dyspnea, anorexia and insomnia). This questionnaire consists of 30 multiple-choice questions.

The samples of EORTC QLQ-C30 (version 3.0) in this study is seen in APPENDIX 5.

In this study, EORTC QLQ-C30 scales will be used to evaluate the quality of life (QoL), including health related quality of life (HRQOL) / general health state (GHS), physical functioning and role functioning, of patients with advanced osteosarcoma who receive SHR-1210 combined with apatinib mesylate. The following endpoints are included:

- TTD, defined as time from enrollment to first deterioration, as determined by

following subscales of EORTC QLQ-C30 subscales (decreased by ≥ 10 points from baseline), at least maintained for two consecutive time points, or maintained for one-time point but death in the following three weeks (for any reason):

- HRQOL/GHS
- Physical functioning
- Role functioning
- Average scores and average change from baseline in all the subscales of EORTC QLQ-C30 (by cycle);

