| 
combined with SHR-1210;
 | 
from baseline maintained for two consecutive time points, or one time-point followed by death [from any cause] within 3 weeks):
 
 - Global health status - Physical Functioning - Role Functioning |
| 
 • To explore the correlation between biomarkers and the efficacy of combined therapeutic regimen; | 
 • Average score and its change in the score from baseline in all the subscales of EORTC QLQ-C30 (by cycle); • The correlation of the expression level of PD-L1 and proportion of strong expression of PD-L1 in tumor tissue with the efficacy of mesylate apatinib combined with SHR-1210 (including but not limited to PFS, ORR, OS); |

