5.1.5. Dose Regimen

Each treatment cycle is defined as 4 weeks (28 days). Dose regimens during treatment period are shown in Table 4.

Table 4. Dosing Regimens for Each Treatment Cycle

| | | |
|--|-------------------|---|
| Experimental arm: SHR-1210 combined with apatinib | SHR-1210 | SHR-1210 intravenous infusion at a dose of 200 mg over 30 minutes (no less than 20 minutes and no more than 60 minutes, including a wash-out period), once every two weeks (Q2W), 4 weeks (28 days) as one treatment cycle. The interval between two doses should not be less than 12 days. |
| | Apatinib mesylate | 500 mg, once per day (QD) orally, after meals within 30 min, for continuous administration, 4 weeks (28 days) is one cycle. |

If a subject in the experimental arm (SHR-1210 in combination with apatinib) develops a treatment-related AE that leads to permanent discontinuation of apatinib and the investigator determines that the subject can benefit from SHR-1210 monotherapy, the subjects may continue to receive SHR-1210 monotherapy until meeting the criteria for study treatment termination specified in this protocol, and vice versa. In addition, during the study treatment period, if a subject in the experimental arm develops a treatment-related AE that leads to temporary discontinuation of SHR-1210 or apatinib, the subject may continue to receive monotherapy, and the combination therapy can be resumed only after the toxicity resolves.

≥7 days later after the scheduled date of administration of SHR-1210 will be considered as a dose delay. The subsequent drug administration time will be calculated from the actual date of the previous dose. Subjects will be given the study drug until meet the criteria for termination of study treatment specified in the protocol.

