6.2.2. Cycles 2 and 3

The following examinations/steps or collection of the following information needs to be completed on Day 1 (± 3 days):

- ECOG-PS score (see APPENDIX 2 for details);
- Weight and physical examination of important sites: cutaneous system, respiratory system, cardiovascular system, abdomen and mental state. In addition, physical examination of reactive capillary endothelial proliferation needs to be performed on the experimental arm;
- Vital signs (performed after sitting still for 5 minutes): including temperature, blood pressure, pulse rate and respiratory frequency;
- Hematology: including complete blood count and category (white blood cell, red blood cell, lymphocyte, monocyte, neutrophil, basophil, eosinophil), hemoglobin, platelet count;
- Urinalysis: including white blood cell, red blood cell, urine protein. In case urine protein is $\geq 2+$, 24h urine protein quantification must be added;
- Blood biochemistry: including ALT, AST, total bilirubin, γ -glutamyl transferase (GGT), direct bilirubin, indirect bilirubin, ALP, LDH, albumin, blood urea nitrogen or serum urea, creatinine, blood glucose, amylase (lipase test needs to be added if amylase level is abnormal and clinically significant);
- Blood electrolytes: including potassium, sodium, chlorine, calcium, magnesium, phosphorus;

- Coagulation parameters: including INR and/or PT (if INR can not be collected, PT will be used as the basis for judgment);
- Fecal occult blood test;
- Thyroid function (only performed on C3D1, TSH, FT3, FT4);
- 12-lead ECG (performed after sitting still for at least 5 minutes): heart rate and QTc interval (calculated using Fridericia's formula);
- Immunogenicity and drug concentration: the blood sample will be collected only from SHR-1210 experimental arm (including SHR-1210 combined with apatinib and SHR-1210 alone), 0.5h prior to administration of SHR-1210 on Day 1 of Cycle 2 and 3 (C2D1, C3D1) (the administration time of apatinib needs to be provided by the patient, and it must occur on the same day earlier than SHR-1210 administration).
- Intravenous infusion of SHR-1210 (experimental arm);
- Oral administration of apatinib (experimental arm) (daily, continuously)
- Distribution, verification and recovery of subject's diary;
- Subject's self-evaluation results: it will only performed on C3D1, all the subjects will complete EORTC QLQ-C30 questionnaires prior to administration of study drug and any other study evaluation at clinical centers;

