6.2.3. Cycle 4 and Onwards

The following examinations/steps or collection of the following information needs to be completed on Day 1 (± 3 days):

- ECOG-PS score (see APPENDIX 2 for details);
- Weight and physical examination of important sites: cutaneous system, respiratory system, cardiovascular system, abdomen and mental state. In addition, physical examination of reactive capillary endothelial proliferation needs to be performed on the experimental arm;
- Vital signs (measured after sitting still for 5 minutes): including temperature, blood pressure, pulse rate and respiratory frequency;
- Hematology: including complete blood count and category (white blood cell, red blood cell, lymphocyte, monocyte, neutrophil, basophil, eosinophil), hemoglobin, platelet count;
- Urinalysis: including white blood cell, red blood cell, urine protein. In case urine protein is $\geq 2+$, 24h urine protein quantification must be added;
- Blood biochemistry: including ALT, AST, total bilirubin, γ -glutamyl transferase (GGT), direct bilirubin, indirect bilirubin, ALP, LDH, albumin, blood urea nitrogen [BUN] or serum urea, creatinine, blood glucose, amylase (lipase test needs to be added if amylase level is abnormal and clinically significant);
- Blood electrolytes: including potassium, sodium, chlorine, calcium, magnesium, phosphorus;
- Coagulation parameters: including INR and/or PT (if INR can not be collected, PT will be used as the basis for judgment);
- Fecal occult blood test;
- Thyroid function (once every two cycles, for example, C5D1, C7D1, TSH, FT3, FT4);
- 12-lead ECG (performed after sitting still for at least 5 minutes): heart rate and QTc interval (calculated using Fridericia's formula);
- Intravenous infusion of SHR-1210 (experimental arm);

- Oral administration of apatinib (experimental arm) (daily, continuously);
- Distribution, verification and recovery of subject's diary; experimental arm: on D1 and D15 of each cycle; control arm: only on D1 from Cycle 4;
- Subject's self-evaluation results: (once every two cycles in the first 12 cycles of therapy, for example, C5D1, C7D1, once every three cycles afterwards). All the subjects will complete EORTC QLQ-C30 questionnaires prior to administration of study drug and any other study evaluation at clinical centers;
- Collect concomitant medications/therapy;
- Collect AE.

The following examinations/steps or collection of the following information needs to be completed on Day 15 (± 3 days):

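### The exploratory time-to-deterioration rule cannot count many drops first seen on a patient's last questionnaire, because its 3-week death window is shorter than the 8- to 12-week gap between forms

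*Protocol*

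**What the plan says.** Protocol section 2 lists TTD as an exploratory endpoint for global health status, physical functioning and role functioning. The event is a fall of at least 10 points from baseline, "maintained for two consecutive time points, or one time-point followed by death [from any cause] within 3 weeks". Section 7.4.1 repeats the rule: "at least maintained for two consecutive time points, or maintained for one-time point but death in the following three weeks".

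The calendar is set elsewhere. A cycle is 28 days (section 5.1.5). After the Day 1 form of cycle 1, section 7.4 has patients "repeat the above procedure on Day 1 of every two cycles in the first 12 cycles, and Day 1 of every three cycles afterwards", with the end-of-treatment visit as the last occasion. Section 6.2.2 places the only form of cycles 2 and 3 at C3D1. Section 6.2.3 continues "once every two cycles in the first 12 cycles of therapy, for example, C5D1, C7D1, once every three cycles afterwards". Section 6.3 includes a questionnaire at the end-of-treatment visit, and the follow-up procedures in section 6.4 include none.

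Section 10.4.7 analyses TTD with a Cox model and a Kaplan-Meier curve.

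**The concern.** A death limb in a confirmation rule is there for patients who die before they can complete the confirming form. To do that, it has to span the time until that form is due. Here it is 3 weeks against a scheduled gap of 8 and later 12 weeks.

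The second gap in the rule is the end of data collection. No form follows the end-of-treatment visit, so a drop that first appears there has no possible second time point. Progression and intolerable toxicity are among the protocol's reasons to stop treatment (section 4.4.1), and quality of life may well fall around that moment. If it does, the patients lost as events are lost because they were deteriorating, and the censoring is informative. In a single-arm trial no comparison arm carries the same bias, so the whole of it stays in the reported TTD.

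**Working it through.** The plan gives no figure for TTD, so there is none to reproduce. The check has three parts.

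**1. Intervals (sections 5.1.5, 6.2.2, 6.2.3, 7.4)**

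- Gap in the first 12 cycles: 2 × 28 = 56 days (8 weeks). Later gap: 3 × 28 = 84 days (12 weeks).
- Forms after baseline fall on days 57, 113, 169, 225 and 281, then every 84 days, plus the end-of-treatment form.
- Death window: 21 days. Covered: 21/56 = 37.5%, later 21/84 = 25%. Uncovered: 62.5%, later 75%.
- With exponential survival instead of evenly spread deaths, the share of deaths before the next scheduled form that fall outside the window is 1 − (1 − e^(−3λ)) / (1 − e^(−gλ)), where g is the gap in weeks. At the earlier apatinib trial's median OS of 8.77 months (section 10.1; 4.345 weeks per month), λ = ln 2 / (8.77 × 4.345) = 0.0182 per week. For g = 8 this is 1 − 0.053/0.135 ≈ 0.61, and for g = 12 it is 1 − 0.053/0.196 ≈ 0.73. Over the OS confidence limits (6.73 to 16.70 months) the ranges are 60-62% and 72-74%.
- These shares apply only to patients who die before the next scheduled form without an end-of-treatment form in between.

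**2. The rule applied to three patients**

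- Down at day 113, dies on day 145 with no further form: 145 − 113 = 32 days, more than 21. Not an event.
- First down at an end-of-treatment visit on day 130, dies on day 200: 200 − 130 = 70 days, more than 21, and no later form is scheduled. Not an event.
- Down at day 57 and again at the end-of-treatment visit: event.

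**3. Illustrative simulation on the protocol's calendar**

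Assumptions, none of them fixed by the protocol for this trial: exponential time on treatment with median 4.44 months (the earlier trial's PFS); survival after treatment with median 8.77 − 4.44 = 4.33 months; drops are permanent; a patient who meets neither limb is censored at the last form. The comparator counts every recorded drop, including one on the last form.

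| Onset of the drop | Recorded drops not counted |
|---|---|
| Unrelated to stopping treatment | about 13-14% |
| All within the last 8 weeks of treatment | about 58% |
| All within the last 12 weeks | about 47-48% |
| All within the last 16 weeks | about 41% |

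A variant in which 15% die on treatment without an end-of-treatment form gives 12-14% for unrelated onset.

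For unrelated onset the deterioration-free curve rises by about 3-4 percentage points. At an onset median of 4 months, for example, it is 0.525 under the plan's rule at day 113 and 0.487 if last-form drops count: 0.525 − 0.487 = 0.038. The median can move only with the questionnaire calendar. It shifts by one form at onset medians of 4, 6 and 8 months and stays put at 3 and 5.

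Widening the death window is not enough by itself. With a 56-day window, 48%, 39% and 34% of drops are still uncounted in the three late-onset scenarios, because patients who stop treatment and live longer have no further form.

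**The case against.** The strongest reply is that the SAP is not shown. Section 10 lets it define analysis variables and override the protocol, and section 10.4.4-10.4.7 leaves further analysis detail to it. The protocol never says that these patients are censored. This stands as far as the censoring date goes. It does not rescue the event definition: the protocol fixes that in two places, and a patient who meets neither limb is a non-event unless the definition itself changes.

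Second, end-of-treatment forms can come less than 8 weeks after the previous form and confirm an earlier drop, and section 6.6 allows treatment, with its visits, beyond progression. Both points are right and reduce the loss. The end-of-treatment forms are already in the simulation; treatment beyond progression is not.

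Third, requiring confirmation is a legitimate guard against transient dips, and counting an unconfirmed last score gives some of that up. This also stands, and it is why the strict version should remain as a sensitivity analysis.

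Two stronger readings are tempting. A reader might infer that median TTD is inflated from 3.7 to 5.6 months. Those are days 113 and 169, two adjacent forms, and the jump arises because a difference of about 4 points happens to straddle 0.50 at one assumed onset median. A reader might also infer that around half of all deteriorations are lost. That follows only when every onset is placed shortly before stopping, and nothing in the protocol establishes such a pattern.

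**Conclusion.** The rule as written does not fit the questionnaire calendar. The direction of the bias is clear: every recorded drop that meets neither limb lengthens TTD, on all three selected scales. The size cannot be derived from the documents. On the assumptions stated, about 13-14% of recorded drops are not counted if onset is unrelated to stopping, the curve rises by about 3-4 percentage points, and the median moves by at most one questionnaire step. The loss grows if quality of life falls around treatment stop; 41-58% marks an extreme scenario and is no forecast.

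TTD is exploratory. No hypothesis, alpha or sample size depends on it, and the primary conclusion is unaffected. This is a low-priority correction.

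**What to change.** In sections 2 and 7.4.1, define deterioration as a fall of at least 10 points from baseline that is either confirmed at the next questionnaire or present at the last available questionnaire, when no later one exists because of end of treatment or death. If a separate death limb is kept, set its window to the interval to the next scheduled questionnaire: 8 weeks in the first 12 cycles, 12 weeks afterwards. Report the strict two-time-point version as a sensitivity analysis.

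The cost is one changed sentence in each of the two sections and one extra table; no new data are needed. The downside is that some transient drops on the last form will count as events. Comparing the main and the strict results shows how much depends on them.
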